Early identification of Malignant Brain edema in laRge Artery oCclusive
stroke after Endovascular therapy (EMBRACE study)

Protocol Version Number and Date: 1.0, March 20, 2024

Background

Stroke is a significant global cause of death and disability. Endovascular thrombectomy (EVT) is currently the best treatment for acute large vessel occlusion stroke (ALVOS), as it can greatly reduce mortality and improve patient outcomes. However, only half of patients who undergo EVT achieve functional independence, and malignant brain edema (MBE), a severe complication, can occur after the procedure, leading to a poor prognosis. Previous studies have confirmed the effectiveness of early decompressive hemicraniectomy in reducing morbidity and mortality in patients with malignant brain edema. Therefore, identifying high-risk patients for MBE can help clinicians make appropriate triage and early intervention decisions, potentially saving patients' lives.

Predictive factors for post-ischemic stroke brain edema have been widely discussed, and reliable early predictive indicators have been identified, such as age, early consciousness disorders, baseline National Institutes of Health Stroke Scale (NIHSS), atrial fibrillation, hypertension, baseline blood glucose, and the level of reperfusion after EVT. Radiological factors, such as the Alberta Stroke Program Early CT Score (ASPECTS), collateral circulation rating of arteries, venous outflow status, CT perfusion core infarct volume, perfusion-based collateral status, and clot burden, are closely associated with the occurrence of MBE post-EVT. However, due to individual differences and multiple factors affecting MBE, a single factor cannot effectively predict MBE. Establishing a clinical risk prediction model can effectively identify high-risk populations for MBE at an early stage.

Aim

To design and validate a predictive model for MBE after EVT.

Design

Study Type: Observational [Patient Registry]

Time Perspective: Prospective

Study population

The study is a multicenter, prospective, observational clinical registry study, commenced on April 1, 2024, and is expected to end in June 2027. Participants were ALVOS patients undergoing EVT treatment in neurology departments from multiple stroke centers. The data from Zhejiang Provincial People's Hospital compose the model training cohort, while data from other centers serve as an independent external validation cohort. The protocol of the study has been approved by the human Ethics Committee of Zhejiang Provincial People's Hospital (KY2024058). All clinical investigations will be conducted according to the principles set in the Declaration of the Helsinki.

Inclusion Criteria:

- (1) Age > 18 years old;
- (2) Onset of stroke to hospital admission < 24 hours;
- (3) Admission with a head CT scan ruling out hemorrhage;
- (4) Patients undergoing CT perfusion scan before treatment;
- (5) Confirmation of internal carotid artery (ICA) or middle cerebral artery (MCA) occlusion or tandem occlusion by Digital Subtraction Angiography (DSA) and subsequent EVT;
- (6) complete 3-months follow-up.

Exclusion Criteria:

- (1) Poor quality of preoperative CT perfusion imaging;
- (2) Posterior circulation occlusion or isolated anterior cerebral artery occlusion;
- (3) Presence of other severe diseases such as malignant tumors, severe organ failure, or other life-threatening conditions with an expected survival period of less than 90 days;
- (4) Incomplete imaging and clinical data.

Procedures

All ALVOS patients will undergo comprehensive evaluation by neurologists at admission to the stroke center to obtain baseline data from clinical and laboratory examinations. Multimodality CT, including head non-contrast CT (NCCT), CT perfusion (CTP) and CTP-derived multiphase CT angiography (CTA), will be performed to assess whether patients are eligible for EVT. After EVT, all patients will be transferred to the neuro-intensive care unit for close perioperative and postoperative care to ensure stability of vital signs and implementation of comprehensive monitoring and management. This includes daily neurological assessments, monitoring of vital signs and oxygenation, and management of endotracheal intubation. Once the patient's vital signs stabilize or after the patient is extubated, they will be transferred to the neurology stroke care unit for further treatment. In principle, this trial does not involve the selection and intervention of therapeutic drugs. Within 24 hours post-EVT, patients will undergo repeat head NCCT to exclude hemorrhage and evaluate surgical outcomes. Antiplatelet therapy may be considered based on the patient's specific condition but should be cautiously selected in clinical practice and closely monitored to prevent bleeding complications. In case of signs of hemorrhagic transformation, physicians may adjust the antiplatelet therapy regimen at their discretion, potentially reducing the dose or delaying antiplatelet treatment. Additionally, regular in-hospital follow-up head NCCT scans will be performed on patients at day 3, to monitor disease progression and adjust treatment plans promptly.

Imaging protocol

Head NCCT is performed on a Toshiba Aquilion 320-slice CT scanner (Toshiba Medical Systems) using the following acquisition parameters: 120 kV, 128 mAs, scan coverage of 240 mm, and scan width of 5 mm. Simultaneously, 4-dimensional time-resolved whole-brain CTA and whole-brain CTP can be acquired. Lohexol (45 mL) (Medrad Stellant D SCT-212; Bayer Healthcare) is injected at a rate of 5

mL/second, followed by a 30 mL saline flush at an injection rate of 4 mL/second. All perfusion parameters are analyzed using post-processing software.

Radiological assessments

The imaging variables collected in this study involve arterial, venous and perfusion status variables, including NCCT-ASPECTS, ischemic core volume, the penumbra volume, collateral status based on CTP and multiphase CTA, clot burden score, and venous outflow status. Imaging evaluations will be performed by imaging physicians who are blind to the clinical information.

CT perfusion assessment

Areas with relative cerebral blood flow (rCBF) <30% is defined as the ischemic core. The penumbra volume is calculated by subtracting the ischemic core volume (lesions with rCBF <30%) from the perfusion lesion volume (delay time threshold >3 seconds). The collateral index is defined as the volume of tissue with delay time (DT) >6 s divided by the volume with DT >2 s.

Clot burden score

We use a CBS for the anterior circulation to quantify the extent of ipsilateral intracranial thrombus, allotting major arteries 10 points for the presence of contrast opacification on CTA. Two points each is subtracted for the absence of contrast opacification in the complete cross-section of any part of the proximal M1 segment, distal M1 segment, or supraclinoid ICA, and 1 point each for M2 branches, A1 segment, and infraclinoid ICA. Partial filling defects suggesting stenosis or non-occlusive thrombus are rated as patent. A score of 10 indicates the absence of a visible occlusion on CTA, while a score of 0 indicates occlusion of all major intracranial anterior circulation arteries.

Venous outflow assessment

The outflow status of the sphenoparietal sinus, superficial middle cerebral veins, and intracerebral veins will be evaluated. Venous opacification will be graded per vein using a three-point scale based on baseline CT angiography:

- 0: Complete absence of cortical vein opacification
- 1: Moderate opacification (attenuation of one of the target veins on the contralateral side)
- 2: Full opacification.

Clinical assessments

We will record the demographic data (gender, age, hypertension, diabetes, history of atrial fibrillation), site of occlusion, baseline systolic and diastolic blood pressure, prior IVT administration, baseline NIHSS score, NIHSS score at discharge, modified Rankin Score (mRS) at discharge, and TOAST stroke etiology (Trial of ORG 10172 in Acute Stroke Treatment) of each participant. Hematological laboratory results will include baseline glucose, baseline white blood cell count, baseline neutrophil count, baseline hemoglobin, and platelet count. The EVT operator will record the time from stroke onset to puncture (OTP), time from puncture to recanalization (PTR), and degree of blood flow restoration. The occluded vessel will be determined based on intraoperative angiography results, and reperfusion level will be graded using the modified Thrombolysis in Cerebral Infarction (mTICI) score, with complete reperfusion defined as mTICI 2b-3. Clinical assessments will be conducted by neurologists unaware of the clinical diagnosis.

Study groups

- training set

To determine potential predictive factors, imaging and clinical parameters will be enrolled into LASSO regression analysis, which effectively eliminated several irrelevant or multicollinearity independent variables to reduce high-dimensional data. The multivariable logistic regression analysis will be applied to determine the

variables predicting MBE, and the results will be used to create a predictive model based on the training set.

- validation set

The predictive model will be further validated in the validation set.

Outcome assessment

Primary Outcome Measures:

The occurrence of MBE: Patients developed MBE within 3 days post-EVT

Secondary Outcome Measures:

1. The follow-up mRS scores of enrolled patients at 90 days since stroke onset.
2. Evidence of parenchymal hemorrhage (PH type) on cranial imaging during hospitalization.

Sample size

In this study, predictive model will be constructed using the EVT database from Zhejiang Provincial People's Hospital as a training cohort, and prospective data from other centers will be used to validate the performance of predictive model. We will randomly select 70% of the patients from the Stroke Center EVT database at Zhejiang Provincial People's Hospital as the training cohort, while the remaining 30% will constitute the internal validation cohort. Within the training cohort, our aim will be to analyze imaging and clinical parameters when constructing the predictive model.

Given the requirement of at least 10 events per candidate variable for model establishment, a minimum of 200 MBE patients is necessary in the training cohort to ensure stable model estimation. Based on a study design with a sample ratio of 7:3 for the training and internal validation sets, at least 290 MBE patients will be required in this study at Zhejiang Provincial People's Hospital. The external validation set will require 100-200 positive samples; considering an approximate 20% incidence rate of MBE in anterior circulation EVT patients, this study will need to include at least 1950 EVT patients.

Statistical analysis

Compare baseline clinical and imaging data of EVT patients with and without MBE across the training, internal validation, and external validation sets. Continuous variables conforming to a normal distribution will be described using means and standard deviations, while those not conforming will be described using medians and quartiles. Categorical variables will be expressed as percentages.

In the training set, factors influencing MBE will be analyzed. Continuous variables will be analyzed using Student's *t*-test or Mann-Whitney U test, while categorical variables will be analyzed using chi-square test and Fisher's exact test. Collinearity among variables will be assessed using Variance Inflation Factors (VIFs), where VIF <10 and Tolerance >0.1 indicate no significant collinearity. Variables with a significance level of *P* <0.1 in univariate analysis will be incorporated into logistic regression analysis using forward stepwise selection method, and odds ratios (ORs) and 95% confidence intervals (CIs) will be calculated. Factors with *P* < 0.05 will be included as independent predictors of MBE in the model. After constructing the predictive model, it will be converted into a dynamic nomogram and deployed on a webpage, generating a dynamic nomogram URL.

The dynamic nomogram URL will be used to externally validate EVT data from other stroke centers and will collect data. The area under the receiver operating characteristic (ROC) curve (AUC) will be used to evaluate the ability of the predictive model to identify high-risk MBE patients after EVT in the training, internal and external validation sets, and corresponding 95% CIs will be calculated. Calibration plots and the Hosmer-Lemeshow goodness-of-fit test will assess the consistency between actual MBE occurrence and predicted MBE risk probability in EVT patients. Decision curve analysis (DCA) will determine the clinical net benefit of the model at different risk threshold probabilities in the three sets.

Statistical analyses will be performed using IBM SPSS Statistics software (version

26.0; IBM Corporation, Armonk, NY, USA) and R software (version 4.3.1, R Development Core Team, Vienna, Austria).

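### Complete three-month follow-up is a condition of entry to a model that predicts a three-day outcome, so patients with known outcome are dropped on future information

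*Protocol*

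**What the plan says.** Under Study population, inclusion criterion (6) of the Protocol is "complete 3-months follow-up". It stands beside the baseline criteria and applies to the whole study, and so to the training, internal validation and external validation sets.

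Under Outcome assessment, the primary outcome, which is the one the model predicts, is "Patients developed MBE within 3 days post-EVT". The Procedures section states that "regular in-hospital follow-up head NCCT scans will be performed on patients at day 3". One of the two secondary outcomes needs three months: "The follow-up mRS scores of enrolled patients at 90 days since stroke onset". The other, parenchymal hemorrhage, is assessed during the hospital stay.

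Exclusion criterion (4) removes patients with "Incomplete imaging and clinical data". The items listed under Clinical assessments include some that arise after the time of prediction: "NIHSS score at discharge, modified Rankin Score (mRS) at discharge".

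The Background gives the intended use: "identifying high-risk patients for MBE can help clinicians make appropriate triage and early intervention decisions". The Sample size section rests on an incidence, "considering an approximate 20% incidence rate of MBE in anterior circulation EVT patients".

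**The concern.** A prediction model should be developed and validated in patients who can be identified when the prediction is made. Whether three-month follow-up will be completed cannot be known then, and it is not needed to establish a three-day outcome. As written, a patient with a day-3 scan and a known MBE status leaves the primary analysis because of something that happens, or fails to happen, up to almost three months later.

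Exclusion (4) can have the same effect where the only missing items arise after prediction, such as the discharge NIHSS or discharge mRS. Its effect on missing baseline predictors or a missing day-3 scan is a different question and is not raised here.

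At stake is calibration, meaning the absolute risks that the nomogram reports. If loss depends on MBE status, those risks are shifted for the patients the tool is meant for. Because the same criteria govern every set, the planned calibration plots and Hosmer-Lemeshow test would be run in patients selected in the same way. The event count would also move away from the 20% incidence used for the sample size.

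This cannot be left to an SAP: an SAP can define analysis sets only among patients whom the eligibility criteria admit.

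**Working it through.** **1. The Protocol's own figures (Sample size section).** Training events 200 at a 7:3 split: 200/0.7 = 285.7, stated as 290. Patients at the lead hospital: 290/0.20 = 1450. External validation at the lower end of its range: 100/0.20 = 500. Total 1450 + 500 = 1950, as stated. Expected training events: 0.7 × 1450 × 0.20 = 203, against a stated minimum of 200. The arithmetic contains no allowance for loss to follow-up.

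**2. Effect of the criterion.** Let e1 and e0 be the proportions of MBE and non-MBE patients removed for incomplete follow-up. The Protocol gives neither, so every value below is an assumption. The 20% incidence is taken to hold before this restriction, and loss is taken to depend on MBE status only.

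- Apparent incidence among those kept = 0.2(1 − e1) / [0.2(1 − e1) + 0.8(1 − e0)]
- Multiplier on the predicted odds: k = (1 − e1)/(1 − e0)
- A true risk of 30% has odds 0.4286; predicted risk = 0.4286k/(1 + 0.4286k)
- Expected training events = 0.7 × 1450 × apparent incidence, with 1450 read as the number who meet all criteria

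| Loss in MBE / non-MBE | Apparent incidence | k | True 30% predicted as | Training events |
|---|---|---|---|---|
| 10% / 10% | 0.180/0.900 = 20.0% | 1.00 | 30.0% | 203 |
| 15% / 5% | 0.170/0.930 = 18.3% | 0.895 | 27.7% | 186 |
| 25% / 5% | 0.150/0.910 = 16.5% | 0.789 | 25.3% | 167 |
| 5% / 20% | 0.190/0.830 = 22.9% | 1.1875 | 33.7% | 232 |

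**3. Would the planned checks show it?** A simulation of 2,000,000 patients used one standard normal predictor, a true log-odds slope of 1 and 20% incidence, with the logistic model fitted in the patients kept. For the three unequal-loss rows in turn, mean predicted risk in all otherwise eligible patients was 0.185, 0.169 and 0.225. Observed/expected was therefore 0.20/0.185 = 1.08, 0.20/0.169 = 1.18 and 0.20/0.225 = 0.89. Among the patients kept it was 1.00 each time. AUC was 0.744 to 0.745 in those kept and 0.744 in all.

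**4. Recruitment cost with unrelated loss.** At an assumed equal 10% loss, 1950/0.90 = 2167 treated patients are needed to keep 1950, which is about 217 more.

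**The case against.** The strongest reply is that a possible bias is shown, not an actual one. The Protocol gives no loss rate and no link between loss and MBE, and the scenarios point in opposite directions. A smaller difference does little: 8% against 5% gives k = 0.92/0.95 = 0.968, incidence 0.184/0.944 = 19.5%, a true 30% predicted as 29.3%, and about 198 training events. All of this stands, and the figures should be read as illustrations.

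Much also depends on whether death before 90 days counts as complete follow-up, which the Protocol does not say. If it does, only patients who cannot be traced are removed, and a high loss among MBE patients needs its own justification. If it does not, early deaths are removed as well. Since the Background says MBE leads to a poor prognosis, these would plausibly include more MBE patients. The criterion is misplaced under either reading.

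An observed/expected of 1.00 among the patients kept follows by construction from fitting the model in them. It shows what a check in equally selected patients would report. It does not predict the external validation, where loss that differs between centres could become visible.

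The shortfall below 200 training events is conditional too. The Protocol states its requirement in events and its patient number as a minimum, so recruitment could continue. If the 20% already describes patients with complete follow-up, the counts do not change.

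Lastly, exclusion (4) does not name the discharge items. But its wording is broad enough to cover them, and the Protocol lists them among its clinical data. The point is limited to those items.

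**Conclusion.** The concern holds. It is certain from the text that criterion (6) conditions entry to every set on information later than both the prediction and the outcome, and that the primary outcome does not need it. The size and direction of any bias are not fixed by the Protocol. Loss unrelated to MBE costs only precision and recruitment. Under the assumed unequal losses, observed/expected in all otherwise eligible patients runs from 0.89 to 1.18, with discrimination essentially unchanged, and the planned calibration checks may miss it if loss is similar across centres. These figures assume loss that depends on MBE alone and a 20% incidence before the restriction. The criterion should be changed because the defect is plain and the remedy cheap, not because a large bias has been demonstrated.

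**What to change.** - Delete inclusion (6) as an eligibility criterion and apply the three-month requirement only to the 90-day mRS analysis, with death counted as an observed outcome (mRS 6).
- Include in the primary analysis every otherwise eligible patient whose 3-day MBE status is ascertained, and report how many lack it. This step also uses information from after the procedure, but only what the outcome itself requires.
- Reword exclusion (4) so that missing discharge or 90-day items do not remove a patient from the MBE model.

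The cost is a protocol amendment to two criteria, with no extra patients or visits. Some patients in the MBE model will lack a 90-day mRS, so that secondary analysis will have fewer patients than the primary one. Patients without ascertained 3-day status remain unusable, so the recruitment saving is smaller than the number lost to follow-up; the 217 patients at an assumed equal 10% loss are an upper bound.

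### Exclusion (4) makes data completeness an eligibility rule not limited to baseline predictors, so patients with a known 3-day MBE status can be removed, possibly in relation to outcome

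*Protocol*

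**What the plan says.** The eligibility list (Protocol, Study population, Exclusion Criteria) gives as item (4) "Incomplete imaging and clinical data". It does not say which items count, up to what time, or how much may be missing.

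The primary outcome (Outcome assessment) is "The occurrence of MBE: Patients developed MBE within 3 days post-EVT".

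Some of the data to be collected arise during or after that outcome window:
- Clinical assessments lists "baseline NIHSS score, NIHSS score at discharge, modified Rankin Score (mRS) at discharge" together with the baseline variables.
- Procedures states that "regular in-hospital follow-up head NCCT scans will be performed on patients at day 3", in addition to a repeat scan within 24 hours of EVT.

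Inclusion (6) separately requires "complete 3-months follow-up". The protocol contains no rule for keeping patients with partial data, and none for patients who die before the day-3 scan or before discharge. It gives no expected rate of incomplete records.

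**The concern.** A risk model should be built and tested on everyone to whom it would be applied and whose outcome is known. An eligibility rule based on complete records departs from this in two ways.

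First, it discards patients with a known 3-day outcome because one predictor, such as a single laboratory value, is missing. A later analysis plan cannot repair this, since imputation cannot recover patients who were never eligible.

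Second, read literally, the rule reaches items that arise at or after the outcome. A patient whose MBE was seen on an earlier scan, and who then died or could not have the day-3 scan, has incomplete imaging. A patient who dies in hospital has no examinable NIHSS at discharge. The Background section describes MBE as a severe complication with a poor prognosis, so such gaps could plausibly be commoner in patients with MBE. The study's product is an absolute risk, judged by calibration and decision curves, and differential loss would bias that risk downwards.

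**Working it through.** **1. The plan's own figures (Sample size).** The inputs are 200 MBE events for training, a 7:3 split, 290 MBE events at the development centre, 100 to 200 external events and 20% incidence.
- Development centre: 200 / 0.7 = 285.7, so 286 (stated as 290).
- Total: (290 + 100) / 0.20 = 1950, as stated, using the lower end of the external range.
- This implies 390 MBE and 1560 non-MBE patients. It contains no allowance for patients removed under exclusion (4).

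**2. Equal loss in both groups (assumed rates).** Incidence stays at 20%. If 1950 is counted before the exclusion, expected training events are 290 × 0.7 × (1 − loss) = 203 × (1 − loss):

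| Loss | MBE events kept of 390 | Training events (200 required) | Enrolment needed to keep 1950 |
|---|---|---|---|
| 5% | 371 | 193 | 2053 |
| 10% | 351 | 183 | 2167 |
| 20% | 312 | 162 | 2438 |
| 30% | 273 | 142 | 2786 |

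The last column is 1950 / (1 − loss), rounded up. If 1950 is counted after the exclusion, there is no shortfall in numbers. The 200 events come from the protocol's own premise, "Given the requirement of at least 10 events per candidate variable for model establishment".

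**3. Unequal loss (assumed rates).** Let f1 be the fraction of MBE patients removed and f0 the fraction of non-MBE patients removed.
- Observed incidence = 390(1 − f1) / [390(1 − f1) + 1560(1 − f0)]
- Shift in log-odds = ln[(1 − f1) / (1 − f0)]

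With f0 = 10%, 1404 non-MBE patients remain:

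| f1 | MBE kept | Observed incidence | Log-odds shift |
|---|---|---|---|
| 10% | 351 | 351 / 1755 = 20.0% | 0 |
| 15% | 331.5 | 331.5 / 1735.5 = 19.1% | −0.06 |
| 20% | 312 | 312 / 1716 = 18.2% | −0.12 |
| 30% | 273 | 273 / 1677 = 16.3% | −0.25 |

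In the last row, fitted odds are 0.70 / 0.90 = 0.78 of the true odds.

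**4. What these rows do and do not show.** When removal depends on MBE status alone, logistic regression absorbs it in the intercept and the coefficients are not distorted. Coefficients could move only if removal depends jointly on MBE status and predictors, which this arithmetic does not address.

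**5. Reach of the rule.** The eligibility list applies to every participant, so the training, internal validation and external validation sets are filtered alike. If they lose patients in a similar pattern, calibration in the validation sets can look sound although all three are selected.

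**The case against.** The best defence is that the criterion means baseline predictors only. Radiological assessments lists pre-treatment imaging variables and does not include the day-3 scan, which Procedures presents as monitoring. Study groups and Sample size use very similar wording to the criterion for the candidate predictors. On that reading the discharge and day-3 examples fall away. The reading is possible, but the criterion does not state it, and Clinical assessments lists the discharge scores among the recorded clinical data. Even if accepted, it would still discard patients with a known outcome for one missing predictor.

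A reader might infer four stronger points that the documents do not support:
- **That early deaths and severe cases are removed most often.** The protocol has no data on whose records are incomplete. Death can be scored on the mRS, an NIHSS after death could be treated as not applicable, and missing admission values need not follow severity.
- **That the rule can be applied only once the outcome is known.** This is true of the discharge and day-3 items. Missing admission items can be recognised before day 3.
- **That losses must be very large.** If about 26 items were each 99% complete and independent, 0.99^26 = 77% of patients would remain. Missing items cluster, however: one blood count or one CT acquisition supplies several, so this overstates the loss.
- **That validation cannot reveal the problem.** Centres with different patterns of missing data could differ in calibration, so it may show in part.

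Finally, inclusion (6) also selects on data that arise after the outcome. It is a related but separate problem, and correcting it would leave exclusion (4) in force.

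**Conclusion.** The concern holds in a limited form. Exclusion (4) is an open-ended completeness rule placed in eligibility. It can remove patients whose 3-day MBE status is known, and on a literal reading it can do so because of items that arise after the outcome.

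Whether this biases the model depends on how far removal differs by MBE status, which the documents do not give. The bias in incidence is nil if loss is equal. If MBE patients are lost 1.5 to 3 times as often as others from an assumed 10% base, observed incidence is about 19.1% to 16.3% instead of 20%, with a log-odds shift of about −0.06 to −0.25 and predicted risks correspondingly too low. Selective loss of early deaths and severe cases is plausible but not established. The unnecessary loss of patients and events does not depend on that assumption.

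**What to change.** - Delete exclusion (4) as an eligibility rule. Keep every otherwise eligible patient whose MBE status within 3 days can be determined from any available scan or recorded event.
- State that missing discharge items, or a missing day-3 scan after MBE is established, do not affect inclusion.
- Handle missing baseline and procedural predictors by multiple imputation within each cohort, with the complete-case analysis as a sensitivity analysis.
- Report by cohort the number and baseline features of patients whose MBE status cannot be determined. Some very early deaths may still fall in this group, so the report is needed to judge the selection that remains.

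Limiting the criterion to a named list of baseline items would remove the post-outcome problem but keep the needless loss of patients with a known outcome.

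The cost is one deleted criterion, one analysis paragraph, some imputation work and reliance on a missing-at-random assumption for the predictors. No extra patients or procedures are needed. Inclusion (6) should be dealt with separately.

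### Could NIHSS and mRS at discharge enter the model that predicts malignant brain edema within 3 days?

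*Protocol*

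**What the plan says.** Under Clinical assessments, the items to be recorded for each participant include "baseline NIHSS score, NIHSS score at discharge, modified Rankin Score (mRS) at discharge, and TOAST stroke etiology", alongside demographics, blood pressure and site of occlusion. Under Study groups (training set), "imaging and clinical parameters will be enrolled into LASSO regression analysis". Under Sample size: "Within the training cohort, our aim will be to analyze imaging and clinical parameters when constructing the predictive model". Under Statistical analysis, variables with P<0.1 "in univariate analysis will be incorporated into logistic regression analysis using forward stepwise selection method", and those reaching P<0.05 form the model. None of these sentences names the candidates or the moment at which the prediction is made.

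The primary outcome is worded "Patients developed MBE within 3 days post-EVT". The discharge scores are not listed as outcomes; the secondary outcomes are 90-day mRS and parenchymal hemorrhage. No discharge day is given, but the Procedures section says that "regular in-hospital follow-up head NCCT scans will be performed on patients at day 3".

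**The concern.** A predictor has to be known before the event it predicts. A scan at day 3, while the patient is still in hospital, implies that discharge normally falls after the outcome window closes. NIHSS and mRS at discharge would then partly be consequences of MBE.

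If either score were selected, the model could not serve its purpose of flagging high-risk patients early. Its AUC and net benefit would also tend to look too good. External validation would not correct this, because the same late score could be entered at the other centers. The selection rules work on P values alone, and a P value does not see the order of events.

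**Working it through.** **1. The plan's own figures.** Ten events per candidate and "a minimum of 200 MBE patients is necessary in the training cohort" imply 200/10 = 20 candidates. The 7:3 split gives 200/0.7 = 285.7, so 286 against the stated 290. The total is (290 + 100)/0.20 = 1950, as stated, at the lower end of the 100-200 external events.

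Counting one term per item, the protocol lists 13 clinical, 5 laboratory, 3 procedural and 7 imaging variables: 28 in all, or 26 without the two discharge scores. Neither count is 20, so the sample size neither includes nor excludes these scores. The count may shift by one or two with the handling of collateral status, venous outflow and multi-category items.

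**2. Would the P<0.1 screen stop a discharge score?** With 200 events and 800 non-events (20% incidence), a standardized difference d has noncentrality d × √(200 × 800/1000) = 12.65d. The chance of passing at two-sided 0.1 is about Φ(12.65d − 1.645):
- d = 0.2: Φ(0.885) = 0.81
- d = 0.3: Φ(2.15) = 0.98

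The screen gives no protection, but this is true of any weak variable and is not specific to discharge scores.

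**3. What entry could do (all inputs assumed, binormal).** Take a baseline model with AUC 0.80, so d0 = √2 × z(0.80) = 1.190. For a discharge score with difference d and within-group correlation ρ:

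D² = (d0² − 2ρ·d0·d + d²)/(1 − ρ²), AUC = Φ(√(D²/2))

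| Score alone | ρ = 0 | ρ = 0.4 | ρ = 0.6 | ρ = 0.67 |
|---|---|---|---|---|
| d = 0.8 (AUC 0.714) | 0.845 | 0.810 | 0.801 | 0.800 |
| d = 1.0 (AUC 0.760) | 0.864 | 0.825 | 0.810 | 0.806 |
| d = 1.5 (AUC 0.856) | 0.912 | 0.876 | 0.862 | 0.859 |

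The gain runs from 0 to 0.912 − 0.800 = 0.11. At prevalence and threshold both 0.20, net benefit is 0.2 × (2Φ(D/2) − 1). That is 0.0896 for the baseline model and 0.0896 to 0.1323 combined.

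**4. Would the score stay in at P<0.05?** In simulated logistic models (200 against 800, 500 runs), the score with d = 0.8 stayed in with probability 1.00, 0.98, 0.20 and 0.07 at ρ = 0, 0.4, 0.6 and 0.67. The score with d = 1.5 stayed in every time at ρ = 0.4, 0.6 and 0.67. These models hold one baseline variable plus the score. They do not mimic LASSO or stepwise selection among many candidates.

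**5. The text side by side.** Steps 2 to 4 matter only if a discharge score is offered to the model. On that question:
- The sentence with the discharge scores states what will be recorded. It does not say that each recorded item is a candidate.
- The paragraph that sets the P<0.1 rule opens by saying that it examines what influences MBE. A score that results from MBE does not influence it.
- The paragraph just before it says "Compare baseline clinical and imaging data of EVT patients with and without MBE". The univariate tests then contrast the same two groups within the training set.
- The Background names 13 predictive factors by my count (7 clinical, 6 imaging). The latest is the reperfusion level achieved by the procedure, and none belongs to discharge.
- The title and the Background both frame the task as early identification.

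**The case for a change.** The best case for acting is that the protocol already fixes a selection procedure with thresholds, and that this procedure as written is open. The word baseline qualifies a descriptive comparison, not the selection sentences. It cannot define the candidates anyway, since reperfusion level is expected among them and is known only after the procedure. A stated aim shows intent but is not a rule. The discharge scores have no other role assigned, and closing the gap would take a sentence or two and no new data.

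Part of this stands. The selection sentences do not exclude the scores, and baseline alone does not settle the candidate set. The rest is weaker. The reperfusion argument carries the candidates to the end of the procedure, not on to discharge. A variable may be recorded for description without being labelled an outcome, so the missing label does not make it a predictor. The finished model is to be published as a web nomogram whose inputs are visible, so a request for a discharge score would be plain to any user. The low cost of a clarifying sentence does not show that the plan is wrong without it.

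**Conclusion.** No change to the plan is called for. The literal observation is true: the discharge scores share a list with baseline items, and no prediction time is written down. But this is silence on a detail commonly settled when the analysis plan names the candidates. The surrounding text points one way, and analysts would fill the gap by leaving the scores out.

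Harm needs two further steps: someone must enter a discharge score in a model built for early identification, and the score must survive selection. Even then, the illustrated AUC gain is 0 to 0.11, and retention of the weaker score runs from 7% to 100%. Both ranges rest wholly on assumed values (baseline AUC 0.80, score AUC 0.71 to 0.86, correlation 0 to 0.67, binormal scores even for the ordinal mRS), so they give no size for an error in this plan. The conclusion assumes that discharge normally follows day 3, which the protocol suggests but does not state, and that the candidates are chosen in line with the study's declared purpose.
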